#### **4.4.2.2. Hypothesis 2.**

### *Approach*

To evaluate this hypothesis, we will conduct a prevalence analysis using a multilevel regression model to obtain site-level prevalence estimates of participant mortality using the

general equation:  $\text{logit}(p_{ij}) = X'\beta + \alpha_i$ , where  $x_{ij} = (x_{ij1} \dots x_{ijq})'$  is a vector of  $q$  covariates,  $\beta = (\beta_1 \dots \beta_q)'$  is a vector of fixed effects and  $\alpha_i$  is the random effect for site (Raudenbush & Bryk, 2002). The model will include demographic variables (e.g., race, gender, age, etc.), as well as site-level data and cross-level interactions. The prevalence estimates will be calculated from the predictors in the multilevel regression where:  $\hat{p}_{ijk} = e^{\text{predictor}} / 1 + e^{\text{predictor}}$ . A follow-up evaluation will determine site-level prevalence rates by factors such as MCS and risk status categories, with the formula:  $\hat{p}_{ijk} = \sum_j \frac{n_{ijkl}}{n_{ijk}} \hat{p}_{ijkl}$ , where  $\hat{p}_{ijk}$  is the estimated prevalence of mortality in site  $i$  of risk status  $j$  at time  $k$ ,  $n_{ijkl}$  is the number of participants in site  $i$  that are of MCS (or risk status type)  $j$ , at time  $k$  and belong to demographic group  $l$  (i.e., a particular age, gender, race group),  $n_{ijk}$  is the total population in site  $i$  of risk status type  $j$ , at time  $k$  and  $\hat{p}_{ijkl}$  is the estimated prevalence of patient mortality in site  $i$  that are of risk status type  $j$  at time  $k$  and belong to demographic group  $l$ . We will compare these rates using risk difference and rate ratios (Agresti, 2013).

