## **1. OBJECTIVES**

### **1.1. Hypotheses**

A standardized clinical protocol that selects patients for MCS based on shock severity, will be non-inferior with respect to 1 month and 1 year mortality, compared to standard clinical protocols that do not differentiate based on shock severity in adult patients following an initial diagnosis of acute myocardial infarction complicated by cardiogenic shock (AMICS).

Those patients with shock that is not severe and do not have MCS, have a mortality rate that is similar or better than patients who have severe shock and receive MCS.

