Specifically, our goal is, first, to examine the degree to which a standardized clinical protocol that selects patients for MCS based on shock severity will be non-inferior with respect to mortality when compared with a standard clinical protocol that does not differentiate based on shock severity among adult patients following an initial diagnosis of AMICS. Second, our goal is to determine the degree to which mortality rates of patients with AMICS differ on MCS exposure.

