#### Expected results

We expect patients with shock that is not severe and do not receive MCS, have a mortality rate that is similar or better than patients who have severe shock and receive MCS.

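### Hypothesis 2 contrasts two joint severity-by-MCS groups, but the analysis in section 4.4.2.2 nowhere specifies that contrast and, read literally, compares rates by one factor at a time

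*Protocol*

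**What the plan says.** Section 1.1 states the second hypothesis: "Those patients with shock that is not severe and do not have MCS, have a mortality rate that is similar or better" than in the comparator. The Expected results under 4.4.2.2 repeat the pair, setting "patients with shock that is not severe and do not receive MCS" against "patients who have severe shock and receive MCS". Each group is defined by two conditions at once, severity and MCS.

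Section 4.4.2 (Analytic strategy) gives the second goal differently: to "determine the degree to which mortality rates of patients with AMICS differ on MCS exposure". Severity has dropped out.

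The Approach under 4.4.2.2 fits a multilevel logistic model for mortality and lists its content: "The model will include demographic variables (e.g., race, gender, age, etc.), as well as site-level data and cross-level interactions". It continues: "A follow-up evaluation will determine site-level prevalence rates by factors such as MCS and risk status categories". The formula that follows has four indices: site i, group j, time k and demographic group l. The clinical grouping sits in j alone, and the count in the numerator is of participants "that are of MCS (or risk status type" j. The other terms of the formula are defined by risk status only. The rates so obtained are compared by risk difference and rate ratio. Shock severity is not named anywhere in that paragraph.

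**The concern.** The hypothesis concerns two cells of a two-by-two table of severity by MCS. A single index that is either MCS or risk status gives the margins of that table. The MCS margin sets all patients without a device against all patients with one, with severities mixed. The risk-status margin mixes device use, and the visible text does not say that risk status means the shock-severity class.

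If an analyst follows the formula as printed, the risk difference and rate ratio reported for Hypothesis 2 describe other groups. In particular, severe patients who received no device would be pooled with the non-severe patients whom the hypothesis is about. Hypothesis 2 is one of only two hypotheses in the protocol. The primary outcome and the sample size are not affected.

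**Working it through.** **The plan's own figures.** Hypothesis 2 has no sample size, margin or assumed rate to reproduce. The 672 patients in the Power paragraph belong to Hypothesis 1. Assuming 1:1 allocation, that figure does reproduce: (0.397 × 0.603 + 0.31 × 0.69) × (1.960 + 0.842)² / (0.413 − 0.31)² gives 336 per group after rounding up, 672 in all. It has no bearing on this point.

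**Texts side by side.**

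| Place | Groups compared |
|---|---|
| 1.1 and Expected results of 4.4.2.2 | not severe without MCS, against severe with MCS |
| 4.4.2, second goal | by MCS exposure |
| 4.4.2.2, formula | levels of j: MCS, or risk status |
| 4.4.2.2, fallback regression | between groups, not named |

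Only the first row states the joint pair, and no analysis text carries it through.

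**When the two contrasts agree.** Let N0 and NM be mortality in non-severe patients without and with MCS, and S0 and SM the same for severe patients. Let w0 be the share of severe patients among those without MCS, and w1 the share of non-severe patients among those with MCS. Then

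MCS-only difference = (N0 − SM) + w0 × (S0 − N0) − w1 × (NM − SM).

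The first bracket is the hypothesised contrast. The other two terms vanish for certain only if w0 = w1 = 0, that is, if severity fully determines MCS use. Section 4.1 has providers follow the algorithm where clinically suitable, so some off-pattern patients must be allowed for.

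**Illustration (all rates assumed; none is in the documents).** 60% of patients severe; SM = 45%, S0 = 65%, N0 = 20%, NM = 40%. The hypothesised contrast is 20% against 45%: −25 points, ratio 0.44.

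If 80% of severe and 10% of non-severe patients receive MCS:
- No MCS: (0.36 × 0.20 + 0.12 × 0.65) / 0.48 = 31.3%
- MCS: (0.48 × 0.45 + 0.04 × 0.40) / 0.52 = 44.6%

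| MCS use, severe / not severe | Off-pattern share | MCS-only difference | Ratio |
|---|---|---|---|
| 90% / 5% | 8% | −18.7 points | 0.58 |
| 80% / 10% | 16% | −13.4 points | 0.70 |
| 70% / 20% | 26% | −8.0 points | 0.82 |

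**Other assumed rates.** With half the patients severe and SM = 45%, S0 = 60%, NM = 30%, N0 = 20%, the joint difference is again −25 points. The MCS-only difference is −25.0, −19.5, −14.0, −8.5 and −3.0 points when 0, 10, 20, 30 and 40% of patients are off-pattern. The severity-only difference stays between −25.0 and −27.0 points. So in this example a literal reading does most harm when j is taken as MCS.

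**Can the joint rates be recovered from the margins?** No. Take assumed cell sizes of 236 (severe, MCS), 100 (severe, no MCS), 100 (not severe, MCS) and 236 (not severe, no MCS). One fixed set of margins (MCS 43.5% against no MCS 26.0%; severe 43.5% against not severe 26.0%) fits joint pairs of 11.5% against 36.5%, 20.0% against 45.0%, and 28.5% against 53.5%. The ratios are 0.32, 0.44 and 0.53. With these equal cell sizes the difference happens to be −25 points each time; the rates and the ratio are not determined.

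**The case against.** The strongest reply is that the paragraph opens by saying it evaluates this hypothesis, that its list of factors is open-ended and joins MCS and risk status with *and*, and that one index can hold joint categories. The fallback's groups can likewise be read as the pair named just above it. This stands in part. A reader might infer that the hypothesised contrast will never be computed; the documents do not support that, because cross-classification is neither stated nor excluded. What they support is that the contrast is not specified, and that the printed formula and the second goal in 4.4.2 point elsewhere.

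A reader might also infer that risk status is defined nowhere in the protocol. That cannot be asserted: Appendix A appears only as a heading in the text available, and Appendix C is not in it. It can be said that the paragraph using the term does not tie it to shock severity.

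It may further be said that the levels of j are a matter for the statistical analysis plan. That would hold had the protocol been silent. Instead it prints an estimator, defines its indices and restates the aim, and a plan that followed them faithfully would inherit the mismatch.

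Finally, the size of the effect is wholly assumed, and with full adherence to the algorithm the contrasts coincide. Both statements are correct. Hypothesis 2 has no margin or power target, and the sign is unchanged throughout the examples, so no conclusion is shown to reverse.

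**Conclusion.** The point holds as a mismatch between hypothesis and specified analysis. Sections 1.1 and 4.4.2.2 (Expected results) name two joint groups; the second goal in 4.4.2 names MCS exposure alone; and the formula in 4.4.2.2 groups by MCS or by a risk status not linked to severity. Read literally, it yields a different contrast unless severity fully determines MCS use.

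The size of the distortion is unknown from the documents. Under the first set of assumed rates, −25 points would appear as −18.7 to −8.0 points by MCS alone; both the amount and the direction rest on those rates and on the off-pattern share. It would be going too far to infer that the wrong groups will certainly be analysed or that the finding would change sign. The paragraph should be corrected before analysis, but the primary analysis does not depend on it.

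**What to change.** In section 4.4.2.2:
- Define j as the joint category of the protocol's shock-severity class and MCS use, with four levels, and replace risk status by that class.
- Name the risk difference and risk ratio of *not severe, no MCS* against *severe, MCS* as the Hypothesis 2 estimate.
- Show the other two groups descriptively beside it.
- Let the fallback regression refer to the same two groups.

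In section 4.4.2, reword the second goal to name the same contrast.

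The cost is the rewording of a few sentences, with no change to treatment. It assumes that severity class and MCS use are recorded for each patient. Sections 1.3 and 4.1 imply this for severity, but the list of data elements in Appendix C is not in the text available. The downside is that the off-pattern groups will be small and imprecise. The contrast should therefore be reported pooled over sites and not within each site-by-demographic stratum.

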#### Expected results

We expect patients with shock that is not severe and do not receive MCS, have a mortality rate that is similar or better than patients who have severe shock and receive MCS.

#### Potential problems and alternatives

In the event of unforeseen problems related to the proposed models, we will simplify our approach by comparing the odds of mortality between groups using a multivariate logistic regression to model conditional model-estimated hazard probabilities and corresponding survival probabilities

(Masyn, 2014; Muthén & Masyn, 2005).

## **5. DATA AND SAFETY MONITORING PLAN**

Data collected by the participating sites will be entered into case report forms, then stored and managed in a secure REDCap database hosted by Atrium Health. REDCap (Research Electronic Data Capture) is a secure, web-based application, designed to support data capture for research studies. The REDCap database which will be used for the registry, was built solely for the purposes of this project, and includes only those data elements deemed relevant for measuring and analyzing the objectives of interest.

The protocol and recorded data will be monitored in accordance with the Data Coordinating Center's monitoring plan, and will operate under standard operating procedures set forth by both the Office of Clinical and Translational Research and the Center for Outcomes Research and Evaluation at Atrium Health.

Due to the nature of this project, participation in the registry presents no more than minimal risk to subjects. According to the FDA Guidance for Clinical Sponsors: Establishment and

Operations of Clinical Trial Data Monitoring Committees, this study does not require oversight by a Data and Safety Monitoring Committee.

### **5.1. Data Quality Assurance**

This study will be organized, performed, and reported in compliance with the study protocol, standard operating procedures (SOPs) set forth by the Office of Clinical and Translational Research and the Center for Outcomes Research and Evaluation at Atrium Health, the FDA, and other applicable regulations and guidelines (e.g. GCP).

Data will be collected on electronic Case Report Forms (eCRFs).

The protocol and recorded data will be monitored in accordance with the Data Coordinating Center's monitoring plan. This monitoring will be done by comparing source documentation to the eCRFs.

The study database will be reviewed and checked for omissions, apparent errors, and values requiring further clarification using computerized and manual procedures. Data queries requiring clarification will be generated and addressed by the appropriate research teammates, including the Project Coordinator and/or Principal Investigator. Only authorized personnel will make corrections to the project database, and all corrections will be documented in an electronic audit trail.

Any variation between the two data sets will be discussed with the site's Project Coordinator and Principal Investigator.

### **5.2. Communication Between Sites**

The project steering committee and/or research team will meet on at least a monthly basis, or more frequently as needed. The meetings will take place to discuss any encountered issues, discuss project progress, and to address other project related topics, as appropriate.

Participating sites will be required to report any problem that could affect the validity/integrity of the study data to the Principal Investigator and the Data Coordinating Center. Any problem should be communicated to the Principal Investigator and the Data Coordinating Center as soon as possible.

## **6. STUDY COMPLETION**

### **6.1 Completion**

The study will be considered complete upon the determination of the Principal Investigator or the Institutional Review Board.

## **6.2 Termination**

The study will be terminated upon completion of the enrollment period, or once the risk-benefit ratio becomes unacceptable owing to, for example, results of parallel studies or if the study conduct (e.g. data quality, protocol compliance) does not suggest a positive contribution toward the study objectives.

The Principal Investigator has the right to close the study at any time. Closures should only occur after consultation between involved parties and all affected institutions must be informed as applicable according to local law.

## **7. RETENTION OF RECORDS**

Essential protocol documentation, including all IRB correspondence, will be retained for at least 2 years after the investigation is completed. Documentation will be readily available upon request.

## **8. ETHICAL AND LEGAL ISSUES**

### **8.1 Ethical and Legal Conduct of the Study**

The procedures set out in this protocol, pertaining to the conduct, evaluation, and documentation of this study, are designed to ensure that the Investigator abide by Good Clinical Practice (GCP) guidelines and under the guiding principles detailed in the Declaration of Helsinki. The study will also be carried out in keeping with the applicable local laws and regulation(s).

Documented approval from appropriate agencies (e.g. IRB) will be obtained before the start of the study, according to GCP, local laws, regulations, and organizations.

Strict adherence to all specifications laid down in this protocol is required for all aspects of study conduct; the Investigators may not modify or alter the procedures described in this protocol.

Modifications to the study protocol will not be implemented without consulting the Principal Investigator and the IRB, as applicable. The Principal Investigator must assure that all study personnel, including sub-investigators and other project staff members at external sites, adhere to the study protocol and all applicable regulations and guidelines regarding research both during and after study completion.

The Principal Investigator will be responsible for assuring that all the required data will be collected and properly documented.

## 8.2 Confidentiality

Subject confidentiality will be maintained by the Principal Investigator, the Investigator's associates and co-workers. Confidentiality will be maintained according to ICH E6; 4.8.10, part O: "Records identifying the subject will be kept confidential and, to the extent permitted by the applicable laws and/or regulations, will not be made publicly available. If the results of the study trial are published, the subject's identity will remain confidential."

Participation in the project registry presents no risk, other than breach of confidentiality. To mitigate this risk, only necessary patient identifiers will be captured, and all data used for the project will be stored in a secure REDCap database.

## 8.3 Disclosure of Data

The Principal Investigator, his or her associates and teammates, and the appropriate regulatory agencies may use the information and data included in this protocol as necessary for the conduct of the study. Information contained in this study, and data and results from the study are confidential and may not be disclosed without the written permission of the Principal Investigator.

Local Site Investigators and their research teams will only be able to access PHI from their own patients. However, Lead site teammates and other Project Team and Steering Committee Members may have access to the full registry data, inclusive of external site patient information, as appropriate for the purposes of data accuracy and project oversight. The following project team members will have access to patient medical information, and any necessary information for the completion of the project as outlined in the MOP and this protocol. Data Use Agreements will also be completed for participating sites external to the Coordinating Site's Healthcare System.

### Atrium Health:

- PI
- Co-Investigator(s)
- Data Manager(s)
- Research Nurse(s)
- Data Coordinator(s)
- Statistician(s)
- Other Administrative Teammates such as Steering Committee or Project Team Members

### External Sites:

- Local PI
- Sub-Investigator(s)

- Research Nurse(s)
- Data Coordinator(s)

## **9. PUBLICATION POLICY**

There is no planned interim analysis of the data. A final analysis is planned, for the purpose of presentation and submission for publication of all data at the end of the study enrollment and follow-up periods.

Manuscript(s) and abstract(s) prepared from the data collected during this study will be prepared by the Principal Investigator and select members of the research team. Local Site Investigators will not publish or present results, for reasons beyond site care and quality improvement, without written consent of the Lead Principal Investigator, per the site DUA. Investigators will provide the Principal Investigator with publication or presentation materials (including slides, text of oral or written presentations, and electronic media), at least 30 days in advance of publication/presentation, to allow for review and comment as a means of ensuring confidentiality, accuracy, and objectivity.

## APPENDICES

### APPENDIX A: Cardiogenic Shock Algorithm
